8.1 Sample Size

The sample size for the dose-escalation part of the trial is not based on any statistical assumptions. Rather, it follows the “3 + 3 rule”, a well-established methodology in the design of dose-finding trials in oncology.

This trial plans for cohorts of 3 subjects to be treated at each escalating dose level. After the appearance of a single DLT, the cohort for that dose level will be expanded to 6 subjects.

Therefore, the number of subjects enrolled in the dose-escalation phase of the trial will depend on the number of dose escalation steps needed to reach the MTD. Once the dose of 10 mg/kg is

established as safe, accrual of 10 additional subjects at 3 mg/kg and 10 mg/kg each may be enrolled, for the purpose of generating additional safety, PK and receptor occupancy data, if agreed with the SMC. Once the safety of a dose of 15 mg/kg or 20 mg/kg has been established, the SMC will have the possibility to allow enrollment of up to 15 additional subjects at that dose.

Together with the 6 subjects in the once weekly 10 mg/kg cohort, the expected total sample size in the dose escalation phase of the trial will be up to 66 subjects.

The primary endpoint of the efficacy expansion cohorts is the confirmed BOR according to RECIST 1.1, as adjudicated by an IERC. The ORR will be determined as the proportion of subjects with a confirmed BOR of PR or CR. For each of these cohorts, the trial aims at demonstrating an ORR greater than 10% by means of an exact binomial test with an overall 1-sided alpha level of 0.025.

Based on an assumed ORR of 20% in an unselected population, the sample size of 150 subjects (gastric / GEJ cancer, HNSCC) will provide approximately 91% power, and the sample size of 100 subjects (ovarian cancer) will provide approximately 80% power to reject the null hypothesis of $ORR \leq 10\%$ at the primary analysis.

The sample size of 200 subjects in the urothelial carcinoma efficacy expansion cohort is expected to result in 50-60 PD-L1 positive subjects (based on an expected proportion of 85% PD-L1-evaluable subjects and a proportion of 30 to 35% PD-L1 positive subjects among those that are evaluable). Under the assumption of an ORR of 27% in PD-L1 positive subjects, the sample size of 50 to 60 PD-L1 positive subjects will provide at least 90% power to reject the null hypothesis of $ORR \leq 10\%$.

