8.4 Analysis Sets

The following analysis sets will be defined separately for the dose escalation part and the expansion cohorts in this trial, as applicable:

- **DLT population (dose escalation part):** all subjects with data used for implementing the dose-escalation schedule. These subjects should have received all study treatment administrations in the DLT evaluation period or should have stopped treatment because of DLTs in the DLT evaluation period.
- **Safety population:** all subjects who have received at least 1 dose of trial treatment.
- **Full analysis set (FAS):** all subjects who have received at least 1 dose of trial treatment.
- **PD-L1 positive FAS (urothelial carcinoma efficacy expansion cohort):** all PD-L1+ subjects who have received at least 1 dose of trial treatment.
- **PK population:** All subjects who have completed at least 1 infusion of study drug, and who have provided sufficient concentration measurements.
- **Efficacy population (efficacy expansion cohorts):** all subjects who have received at least 1 dose of trial treatment and have measurable disease at baseline according to IERC assessment.
- **PD-L1 positive efficacy population (urothelial carcinoma efficacy expansion cohort):** all PD-L1+ subjects who have received at least 1 dose of trial treatment and have measurable disease at baseline according to IERC assessment.

- **Efficacy population (primary and secondary expansion cohorts):** all subjects who have received at least 1 dose of trial treatment and have measurable disease at baseline according to investigator assessment.

The definition of the Safety Population and the FAS are identical in this non-randomized study; the Safety population will be used for the safety analysis and the FAS will be used for efficacy analysis. The PD-L1 positive FAS will be the primary analysis population for the primary endpoint of BOR by IERC in the urothelial carcinoma efficacy expansion cohort.

PD-L1 status is assessed by immunohistochemistry. Subjects will be considered PD-L1 positive (negative) for the urothelial carcinoma efficacy expansion cohort if at least (less than) 5% of the tumor cells show PD-L1 membrane staining, respectively. If during assay development (based on generic samples) a different cut-off is determined to be more appropriate, this cut-off may be adapted in the SAP prior to analysis of subject samples from this trial.

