8.5 Description of Statistical Analyses

8.5.1 General Considerations

All data recorded during the study will be presented in individual data listings performed on the safety population. All data will be evaluated as observed, and no imputation method for missing values will be used unless otherwise specified. All data will be presented in a descriptive manner. Confirmatory analyses will be conducted for the primary endpoint of the efficacy expansion cohorts. Each cohort will be analyzed separately, and no multiplicity adjustment across cohorts will be performed. All other analyses are considered as exploratory, even if statistical tests are used.

Descriptive statistics will be used to summarize the trial results, i.e., statistics for continuous variables may include means, medians, ranges and appropriate measures of variability. Qualitative variables will be summarized by counts and percentages. The uncertainty of estimates will be assessed by CIs. Unless otherwise specified, the calculation of proportions will be based on the sample size of the population of interest. Counts of missing observations will be included in the denominator and presented as a separate category if not otherwise specified in the SAP.

The DLT population is the underlying data set for the MTD determination. Safety analyses will be performed on the safety population and efficacy analyses will be performed on the FAS. Sensitivity analysis of the BOR on the efficacy population will be conducted according to further specifications in the SAP. Analyses of PK variables will be performed on the PK population.

The estimation of PK parameters will be performed using WinNonlin® Version 5.0 or higher. All other statistical analyses will be performed using SAS® Version 9.1.3 or higher, or R, Version 2.10.1 or higher.

Full details of the planned analyses will be described in the trial statistical analysis plan (SAP), separately for the dose escalation and the expansion part of the trial.

Unless otherwise specified, the endpoint analyses described in the following will be performed separately for both the dose escalation part and the expansion cohorts of the trial. The primary analysis of the once weekly 10 mg/kg cohort is a safety analysis, which will be done in the framework of the first SMC meeting in this cohort.

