8.5.2.2 Confirmed Best Overall Response per RECIST 1.1 by IERC

The primary endpoint in the efficacy expansion cohorts is the BOR according to RECIST 1.1 and as adjudicated by an IERC (see Section 2.2.2), defined as the best response obtained among all tumor assessment visits after start of trial treatment until documented disease progression, taking into account the following requirement for confirmation. For a BOR of PR or CR, confirmation of the response according to RECIST 1.1 (48) will be required, preferably at the regularly scheduled 6-week assessment interval, but no sooner than 4 weeks after the initial documentation of CR or PR. Confirmation of PR can be confirmed at an assessment later than the next assessment after the initial documentation of PR. A BOR of SD requires that a time point overall response of SD has been determined at a time point at least 37 days after start of study treatment. The response at each scheduled tumor assessment and the BOR will be listed for each subject.

For the gastric / GEJ cancer, HNSCC, and ovarian cancer efficacy expansion cohorts, the primary analysis of the BOR by IERC will be conducted in the FAS, defined as all treated subjects. The number and proportion of BOR (defined as CR + PR) will be tabulated. The ORR will be determined as the proportion of subjects with a confirmed BOR of PR or CR. An exact binomial test will be performed at a 1-sided alpha level of 0.025. The primary analysis is planned 6 months after start of treatment of the last subject in the given cohort. Interim analyses will be conducted after 60% of the subjects in the given cohort have been followed up for 13 weeks. Analyses are considered positive if the lower limit of the 95% confidence interval exceed 10%. Confidence intervals will be constructed using the Clopper-Pearson method.

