In the efficacy expansion cohorts, interim analyses for efficacy are planned 13 weeks after the start of treatment of the 30th subject in all cohorts, 13 weeks after start of treatment of the 60th subject in the ovarian cohort, and 13 weeks after start of treatment of the 90th subject in the gastric / GEJ and HNSCC cohorts. The interim analyses after 60/90 subjects aim to demonstrate efficacy as specified in Section 8.5.2.2. No futility rule is foreseen because the clinical activity of anti-PD-1 / anti-PD-L1 agents in these tumor types is established, and the patient populations are characterized by a high unmet medical need. If efficacy criteria are met at the interim analysis, enrollment will continue to the planned full number of subjects in order to collect further data on the primary and secondary endpoints, especially on the association between PD-L1 expression and efficacy endpoints.

In the RCC cohort, one interim analysis of response will be performed 13 weeks after the start of treatment of the 20th subject of second line RCC.

In addition, in the other secondary cohorts that plan to enroll more than 20 subjects, i.e., the ACC, melanoma, mesothelioma, ovarian cancer and urothelial carcinoma cohorts, an interim analysis of response will be performed 13 weeks after the start of treatment of the 20th subject. Accrual in each cohort may be paused during the interim analysis. If no unconfirmed response according to RECIST 1.1 is observed in a given cohort in the interim analysis, accrual in that cohort will be stopped. In addition, for the ovarian cancer secondary expansion cohort, an interim analysis of response will be performed for internal planning purposes 13 weeks after the start of treatment of the 75th subject.

For the purpose of internal planning and for reporting to regulatory authorities, the primary analysis results of the secondary urothelial carcinoma cohort will be updated. The efficacy endpoints such as BOR, PFS, OS, and safety endpoints such as the occurrence of TEAE will be included for these additional analyses. Interim analyses will be conducted for the 109 subjects enrolled in the urothelial carcinoma efficacy expansion cohort prior to Protocol Amendment 13.

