The results of this analysis may be subject to reporting to regulatory authorities. The interim analysis is considered positive if the lower limit of the 95% CI of the confirmed BOR exceeds 10%. Results will be presented for PD-L1 positive FAS and FAS. Further details will be provided in the SAP.

The sequence of statistical analyses planned for urothelial cancer subjects will consider the objective to evaluate the association between tumor PD-L1 expression and BOR prospectively. In a first step, the secondary urothelial carcinoma cohort served as a “training set” for the identification of a PD-L1 expression cut-off that is most likely to identify a subset of the subject population with enhanced clinical benefit. The PD-L1 expression cut-off was specified prior to any statistical analysis of the PD-L1 expression data from the urothelial carcinoma efficacy expansion cohort. In the next step, the cut-off will be verified by conducting an interim evaluation with data from subjects of the efficacy expansion cohort at 6 months after the last subject’s first dose of study treatment for the 109 subjects enrolled in the urothelial carcinoma efficacy expansion cohort prior to Protocol Amendment 13. In case the cut-offs are not mutually supportive in terms of clinical efficacy endpoints the cut-off could be refined and the remainder of approximately 100 subjects of the efficacy expansion cohort will serve as the “validation set” to qualify the tumor PD-L1 expression cut-off. Otherwise, data from subjects of the urothelial carcinoma expansion cohort will be pooled for the final efficacy analyses of the expansion cohort.

For each primary and secondary expansion cohort, an additional interim analysis may be conducted 13 weeks after the start of treatment of the last subject in that cohort. In general, interim analyses at time points that are not specified in the protocol may be performed for internal planning purposes.

9 Ethical and Regulatory Aspects

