16.1 Primary Endpoint Analyses

The primary endpoint in the efficacy expansion cohorts is the confirmed BOR according to RECIST 1.1 and as adjudicated by an IERC, defined as the best response obtained among all tumor assessment visits after start of study treatment until documented disease progression (taking into account the requirement for confirmation). Only tumor assessments performed before the start of any further anti-cancer treatment will be considered in the assessment of BOR.

For the gastric / GEJ cancer, HNSCC, and ovarian cancer efficacy expansion cohorts, the primary analysis of the BOR by IERC will be conducted in the FAS, defined as all treated subjects. The number and proportion of BOR (defined as CR + PR) will be tabulated. The ORR will be determined as the proportion of subjects with a confirmed BOR of PR or CR. An exact binomial test will be performed at a 1-sided alpha level of 0.025. The primary analysis is planned 6 months after start of treatment of the last subject in the given cohort. Interim analyses will be conducted after 60% of the subjects in the given cohort have been followed up for 13 weeks. Analyses are considered positive if the lower limit of the 95% confidence interval exceed 10%. Confidence intervals will be constructed using the Clopper-Pearson method.

For the urothelial carcinoma efficacy expansion cohort, the analysis of the BOR by IERC will be conducted in the PD-L1 positive FAS followed by the FAS. The number and proportion of BOR (defined as CR + PR) will be tabulated. The ORR will be determined as the proportion of subjects with a confirmed BOR of PR or CR. An exact binomial test will be performed in the PD-L1 positive FAS and in the FAS to determine whether the null hypothesis of an $ORR \leq 10\%$ can be rejected at the 1-sided alpha level of 0.025. Interim analyses will be conducted at 4 and 6 months after the first dose date of last subject of the 109 subjects enrolled in the urothelial carcinoma efficacy expansion cohort prior to Protocol Amendment 13. Respective cut-off dates are 18Jan2016 and 19Mar2016. Analyses are considered positive if the lower limit of the 95% CI of the confirmed BOR exceeds 10%. Confidence intervals will be constructed using the Clopper-Pearson method.

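### The plan promises an overall one-sided alpha of 0.025 per efficacy cohort, but applies the full unadjusted rule at both the formal interim and the final look, so that level is not guaranteed

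*Protocol*

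**What the plan says.** Protocol 8.1 sets the level for each efficacy cohort: "by means of an exact binomial test with an overall 1-sided alpha level of 0.025", against a null response rate of 10% or less.

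Protocol 8.6 makes the second interim confirmatory in the ovarian, gastric/GEJ and HNSCC cohorts: "The interim analyses after 60/90 subjects aim to demonstrate efficacy as specified in Section 8.5.2.2". Section 8.5.2.2 has one success rule for interim and final: "Analyses are considered positive if the lower limit of the 95% confidence interval exceed 10" percent. The urothelial interim on 109 subjects has the same rule: "The interim analysis is considered positive if the lower limit of the 95% CI of the confirmed BOR exceeds 10" percent. In the ovarian, gastric/GEJ and HNSCC cohorts, enrolment continues to full size after a positive interim; the urothelial cohort is planned at 200. A second test therefore follows in each.

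The multiplicity statement in Protocol 8.5.1 concerns cohorts, not looks: "Each cohort will be analyzed separately, and no multiplicity adjustment across cohorts will be performed". SAP (expansion) 16.1 repeats the tests and also splits no alpha.

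For the urothelial cohort, Protocol 8.4 says: "The PD-L1 positive FAS will be the primary analysis population for the primary endpoint of BOR by IERC". SAP 16.1 says that "the analysis of the BOR by IERC will be conducted in the PD-L1 positive FAS followed by the FAS", and it lists interims at 4 and 6 months: "Respective cut-off dates are 18Jan2016 and 19Mar2016".

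**The concern.** Each look alone is below 0.025. Adding the second look without adjustment can take the total above the level that 8.1 states. These are the only confirmatory tests in the trial, and Protocol 8.6 says the urothelial interim may be reported to regulatory authorities.

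Three smaller gaps do not enter the calculation:

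- No text makes the urothelial FAS test conditional on success in the PD-L1 positive FAS.
- The protocol names only the 6-month look on the 109 subjects. SAP sections 9 and 16.1 add a 4-month look, and section 9 adds a subset with at least 13 weeks of follow-up. Neither is labelled supportive.
- SAP 16.1 says unadjusted intervals will be calculated as well, but defines no adjusted one.

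**Working it through.** **Inputs.** Null rate 10%, alternative 20%, one-sided 0.025, final n 100, 150 and 200 (Protocol 8.1). Interim n 60, 90 and 109 (8.6). Success means a 95% Clopper-Pearson lower limit above 10% (8.5.2.2), which is the same as reaching the smallest count c with P(X ≥ c | n, 0.10) ≤ 0.025.

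**The plan's own figures.** n = 150: c = 24, power at 20% is 91.1% (stated: about 91%). n = 100: c = 17, power 80.8% (stated: about 80%). Both reproduce with the full 0.025 spent at the final look alone.

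**Two-look error.** Interim subjects are part of the final set, so

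error = P(X1 ≥ c1) + Σ over x < c1 of P(X1 = x) · P(X2 ≥ c2 − x),

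with X1 ~ Bin(n1, 0.10) and X2 ~ Bin(n2 − n1, 0.10).

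| Cohort | Interim rule (error alone) | Final rule (error alone) | Added by final look | Either look |
|---|---|---|---|---|
| Ovarian | ≥12/60 (0.0146) | ≥17/100 (0.0206) | 0.0135 | 0.0281 |
| Gastric/GEJ, HNSCC | ≥16/90 (0.0163) | ≥24/150 (0.0143) | 0.0083 | 0.0246 |
| Urothelial FAS | ≥18/109 (0.0231) | ≥30/200 (0.0163) | 0.0093 | 0.0324 |

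**Incomplete confirmation at the interim.** The table assumes that all eventual responses in interim subjects are already confirmed. If only a share s is, the interim count is Bin(E, s), where E is the number of eventual responders among the n1 interim subjects. The error falls to 0.025 at s = 0.943 (ovarian) and s = 0.944 (urothelial FAS).

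The documents do not give s. As an illustration, assume the NSCLC timing in Protocol 3.5.4 carries over: 7 of 12 first responses at Week 7, and the other 5 assumed at Week 13. Assume also confirmation 6 weeks later and even accrual over A weeks. With the interim 13 weeks after the last interim subject starts, only Week 13 responses in subjects accrued during the final 6 weeks are missed: s = 1 − (5/12)(6/A).

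| A (weeks) | s | 60/100 | 60/101 | 60/102 | 91/150 | 90/156 | 90/157 |
|---|---|---|---|---|---|---|---|
| 26 | 0.904 | 0.0236 | 0.0254 | 0.0273 | 0.0183 | 0.0251 | 0.0266 |
| 39 | 0.936 | 0.0247 | 0.0265 | 0.0284 | 0.0201 | 0.0265 | 0.0280 |
| 52 | 0.952 | 0.0254 | 0.0271 | 0.0290 | 0.0213 | 0.0274 | 0.0289 |

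(c = 17 for 100 to 102; c = 16 for 90 and 91; c = 24 for 150, 156 and 157.)

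The urothelial interim comes 6 months after the last of the 109 subjects starts. On the same timing, with scans at Weeks 7, 13 and 19, every response is confirmed by Week 19. The share is then about 1 and the error close to 0.0324.

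**Realised numbers.** With full confirmation, 91/150 gives 0.0259, 90/151 gives 0.0255 and 90/149 gives 0.0320 (c = 23 at 149). Over interim n 88 to 92 and final n 148 to 152, 19 of 25 combinations exceed 0.025 (range 0.0224 to 0.0343). The break-even share at 90/149 is 84%.

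**PD-L1 positive FAS.** With 30 positives at the interim (Protocol 8.1) and an assumed 55 at the final, the rules are ≥8/30 and ≥11/55, and the error is 0.0224. Over 28 to 32 and 50 to 60 positives it runs from 0.015 to 0.037, with 28 of 55 combinations above 0.025. These urothelial figures cover only the case where all 200 subjects enter the final analysis. The alternative in Protocol 8.6, where the remaining 100 or so validate a refined cut-off, is not modelled.

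**The case against.** The strongest reply is that the excess is small and may not occur.

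- **Gastric/GEJ and HNSCC.** At the planned 90/150 they are within the level. At the illustrative shares, the 19 of 25 falls to 7, 10 and 10, all with a final n of 148 or 149. This stands: at the planned size there is no excess.
- **Ovarian timing.** If two of the five later responses came at Week 19 instead of Week 13, the shares are 0.865, 0.910 and 0.933 and the ovarian error is 0.0225, 0.0237 and 0.0246, never above 0.025. This stands as an equally possible assumption.
- **Urothelial ranking.** The 0.0324 belongs to the second-ranked population, while the primary population at 30/55 is at 0.0224. If the FAS were tested only after PD-L1 success, its error could not be higher than 0.0324. This also stands, but the documents do not state that condition, and the primary population's error depends on how many subjects prove positive.
- **Drift in n.** The documented departures are mostly overshoots outside the efficacy cohorts: 169 MBC and 156 first-line NSCLC subjects against 150 planned, and interims on 23 and 26 subjects instead of 20 in the secondary ovarian and urothelial cohorts. This does not rescue the plan. Overshoot to 101 or 102, or to 156 or 157, exceeds 0.025 at all three illustrative shares. SAP section 9 also records a departure in an efficacy cohort: the first HNSCC interim was cut at 20 subjects instead of 30.

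**Conclusion.** The concern holds. Section 8.1 states an overall level, and no rule in either document secures it across the two looks. At the planned sizes the error is at most 0.0281 (ovarian) and at most 0.0324 (urothelial FAS, second-ranked), both assuming full confirmation at the interim. A realistic ovarian figure is about nominal. The urothelial 6-month look leaves the least room for a discount. Gastric/GEJ and HNSCC comply at exactly 90/150, but only through the discreteness of the exact test. The possible excess is modest. It should be fixed because it contradicts a stated confirmatory error rate and costs little to correct.

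**What to change.** **Interims not yet analysed.** Compute both thresholds from the realised n so that the two looks together stay at or below 0.025, or declare the interim descriptive. Examples, with power at a 20% response rate:

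| Looks | Current thresholds | Tightened thresholds | Error after | Power |
|---|---|---|---|---|
| 60/100 | 12, 17 | 13, 17 | 0.0225 | 82.2% to 81.2% |
| 91/150 | 16, 24 | 17, 24 | 0.0186 | 92.3% to 91.6% |
| 90/149 | 16, 23 | 18, 23 | 0.0246 | 94.2% to 93.7% |

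**Interims already analysed.** Label them descriptive or disclose the two-look error, and do not change a threshold afterwards. This probably applies to the urothelial looks, since SAP version 9.0 is dated 10Feb2017, after both cut-off dates. For reference only, ≥19/109 with ≥30/200 would have given 0.0232 in the FAS.

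**Wording.** State that the urothelial FAS is tested only if the PD-L1 positive FAS succeeds. Label the 4-month look and the subset with at least 13 weeks of follow-up as supportive. Define or delete the word unadjusted in SAP 16.1.

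**Cost.** Protocol and SAP text, no extra patients, and the power changes shown.

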For the urothelial carcinoma efficacy expansion cohort, the analysis of the BOR by IERC will be conducted in the PD-L1 positive FAS (see Section 8.5.3.1) followed by the FAS. The number and proportion of BOR (defined as CR + PR) will be tabulated. The ORR will be determined as the proportion of subjects with a confirmed BOR of PR or CR. An exact binomial test will be performed in the PD-L1 positive FAS and in the FAS to determine whether the null hypothesis of an $ORR \leq 10\%$ can be rejected at the 1-sided alpha level of 0.025. Interim analyses will be conducted for the 109 subjects enrolled in the urothelial carcinoma efficacy expansion cohort prior to Protocol Amendment 13. Analyses are considered positive if the lower limit of the 95% CI of the confirmed BOR exceeds 10%. Confidence intervals will be constructed using the Clopper-Pearson method.

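### Protocol 8.1 promises at least 90% power for 50 to 60 PD-L1 positive urothelial subjects; the planned exact test gives 84.9% to 93.2%, with 84.9% at 51 subjects

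*Protocol*

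**What the plan says.** Protocol 8.1 plans 200 subjects in the urothelial efficacy expansion cohort and expects 50 to 60 of them to be PD-L1 positive, "based on an expected proportion of 85% PD-L1-evaluable subjects and a proportion of 30 to 35% PD-L1 positive subjects" among the evaluable. With an assumed ORR of 27%, it then states that "the sample size of 50 to 60 PD-L1 positive subjects will provide at least 90% power to reject the null hypothesis" of an ORR of 10% or less.

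The population is not a side analysis. Protocol 8.4 says: "The PD-L1 positive FAS will be the primary analysis population for the primary endpoint of BOR by IERC" in this cohort.

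The test is fully specified. Protocol 8.1 sets the aim for every efficacy cohort "by means of an exact binomial test with an overall 1-sided alpha level of 0.025". Protocol 8.5.2.2 applies it here ("An exact binomial test will be performed in the PD-L1 positive FAS and in the FAS"), and SAP (expansion phase) 16.1 says the same ("An exact binomial test will be performed in the PD-L1 positive FAS and in the FAS to determine whether"). The success rule in Protocol 8.5.2.2 is: "Analyses are considered positive if the lower limit of the 95% CI of the confirmed BOR exceeds 10" per cent. On the interval: "Confidence intervals will be constructed using the Clopper-Pearson method".

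**The concern.** The power statement is worded as a floor and attached to a range of sample sizes. For an exact binomial test, power does not rise steadily with n. The critical number of responders is an integer, so each time it steps up by one, power drops and then climbs again. A floor that holds at 50 and at 60 may therefore fail in between, and the statement needs checking at each size.

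What is at stake is the stated chance of success for the primary population of a confirmatory cohort. If the floor fails, the risk of missing a true ORR of 27% is larger than the 10% maximum that the protocol implies.

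**Working it through.** **Inputs**

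- Null ORR 10%, one-sided alpha 0.025, exact binomial test (Protocol 8.1 and 8.5.2.2; SAP 16.1).
- Success if the Clopper-Pearson 95% lower limit exceeds 10% (Protocol 8.5.2.2).
- Assumed ORR 27%, with 50 to 60 PD-L1 positive subjects (Protocol 8.1).
- Comparison figures from Protocol 8.1: about 91% power at n = 150 and about 80% at n = 100, for ORR 20% against 10%.

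**Formulas**

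- Critical count: r = the smallest r with P(X ≥ r | n, 0.10) ≤ 0.025.
- Power = P(X ≥ r | n, assumed ORR), with X binomial.

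**Step 1: reproduce the protocol's other power figures**

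- n = 150, ORR 20%: r = 24, power 91.1% (stated as approximately 91%).
- n = 100, ORR 20%: r = 17, power 80.8% (stated as approximately 80%).

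The exact test reproduces both. A normal approximation without continuity correction, Φ[(√n(p1 − p0) − 1.96√(p0q0)) / √(p1q1)], gives 94.4% and 84.9% and reproduces neither.

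**Step 2: apply the same test at ORR 27%**

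| n | Critical r | Attained one-sided alpha | Power at 27% | Shortfall from 90% (points) |
|---|---|---|---|---|
| 50 | 10 | 2.45% | 90.2% | – |
| 51 | 11 | 1.09% | 84.9% | 5.1 |
| 52 | 11 | 1.26% | 86.7% | 3.3 |
| 53 | 11 | 1.45% | 88.3% | 1.7 |
| 54 | 11 | 1.66% | 89.7% | 0.3 |
| 55 | 11 | 1.89% | 91.0% | – |
| 56 | 11 | 2.14% | 92.2% | – |
| 57 | 11 | 2.42% | 93.2% | – |
| 58 | 12 | 1.12% | 89.3% | 0.7 |
| 59 | 12 | 1.28% | 90.6% | – |
| 60 | 12 | 1.46% | 91.8% | – |

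**Step 3: confirm that the confidence-interval rule gives the same critical counts**

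Clopper-Pearson lower limits around the two steps are: 10/50, 10.03% (passes); 10/51, 9.82% (fails); 11/51, 11.29% (passes); 11/58, 9.87% (fails); 12/58, 11.17% (passes). The two rules agree at every n from 50 to 60.

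**Step 4: where the protocol's own inputs point**

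- At 30% positivity: 200 × 0.85 × 0.30 = 51.
- At 35% positivity: 200 × 0.85 × 0.35 = 59.5.

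The lower expectation falls exactly on the weakest size. If the PD-L1 positive count is treated as binomial out of 200 (my assumption), power averaged over that count is 87.4% at 30% positivity (probability 0.255) and 91.7% at 35% (probability 0.2975).

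**Step 5: what 90% power would need**

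The true ORR that gives 90% power is 28.6% at n = 51, 28.1% at 52, 27.6% at 53, 27.1% at 54 and 27.2% at 58.

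**The case against.** The arithmetic is hard to dispute, so the case on the other side concerns weight and framing.

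- **Some of the misses are trivial.** At n = 54 the value is 89.7%, and at n = 58 it is 0.7 points short. This stands: only 51 to 53 miss by more than one point.
- **These are single-look figures.** The cohort has an interim analysis of 109 subjects, which Protocol 8.1 illustrates with 30 PD-L1 positive subjects, and Protocol 8.6 calls it positive under the same 10% rule. Suppose there are 30 positive subjects at the interim (critical count 8) and a positive result at either look counts. The chance of success is then 86.0% at n = 51, 87.5% at 52, 88.9% at 53, 90.2% at 54 and 90.1% at 58. On that reading 54 and 58 are cured, but 51 to 53 still fail, by up to 4.0 points. The documents do not state outright that the interim counts as a success claim.
- **n = 51 is only one end of the expectation.** At the midpoint, 200 × 0.85 × 0.325 is about 55, where power is 91.0%. The unweighted mean over 50 to 60 is 89.8%. So about 90% is a fair planning value, and the error lies in calling it a minimum.
- **The 27% assumption is itself uncertain.** It rests on preliminary results from the secondary cohort, which Protocol 3.5.5.3 reports as 7 responders among 44 subjects overall. That uncertainty is larger than the shortfall. This is true, but it does not make the stated floor correct under the stated assumption.

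A normal approximation would stay above 90% throughout (91.7% at 50 to 95.0% at 60). It is not the planned test, and it does not reproduce the protocol's other two power figures.

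**Conclusion.** The statement is wrong as written. Under the planned exact test at ORR 27%, single-look power over 50 to 60 PD-L1 positive subjects runs from 84.9% (n = 51) to 93.2% (n = 57). It is below 90% at 51, 52, 53, 54 and 58, materially so only at 51 to 53. At n = 51 the chance of missing a true ORR of 27% is 15.1%, against the 10% maximum implied.

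The pattern would fit a check made only at 50 and 60, but that is an inference. The conclusion rests on the protocol's own null rate, alpha, assumed ORR and test. It does not depend on how the interim is read, since 51 to 53 fail either way. It is a minor point: the correction changes a stated figure, not the design.

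**What to change.** In Protocol 8.1, replace the minimum with a range. For example: approximately 85% to 93% power at the final analysis (single look), depending on the number of PD-L1 positive subjects, with 84.9% at 51.

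The synopsis power statement covers only the 150- and 100-subject cohorts and needs no change. The cost is one sentence: no extra subjects, and no change to the test, alpha or decision rule.
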